## **2.2 Analysis sets**

The **Intent-to-Treat** (ITT) population will consist of symptomatic patients with biallelic deletion mutations of SMN1 (exon 7/8 common homozygous deletions) and 2 copies of SMN2 without the known gene modifier mutation (c.859G>C) who receive an IV infusion of OAV101 at less than 180 days of age.

The **ability to thrive** combined study ITT population will consist of symptomatic patients with biallelic deletion mutations of SMN1, 2 copies of SMN2 without the genetic modifier (c.859G>C), intact swallowing and receiving no enteral (mechanical) nutrition at baseline, who receive an IV infusion of OAV101 and have at least one post-baseline efficacy evaluation.

The all enrolled population will consist of all patients who receive an IV infusion of OAV101.

The safety analysis population will consist of all patients who receive an IV infusion of OAV101.

### **2.2.1 Subgroup of interest**

None.

## **2.3 Patient disposition, demographics and other baseline characteristics**

Patient disposition will be described for all patients of the all Enrolled population. Demographic data and other baseline characteristics will be reported for the Safety population.

### **2.3.1 Patient disposition**

It will be reported if a patient will still be in the study at 14 and 18 months of age, respectively. Among those who discontinued the study prior to reaching the 18 months-of-age visit, the reasons for discontinuation will be enumerated.

---

The number of screened patients who screen failed and the reasons for screen failure (inclusion/exclusion criteria, withdrew consent, and/or other) will be reported. A CSR listing of reason for screen failure will be provided for all patients who screen failed.

### **2.3.2 Demographics and other baseline characteristics**

The age of the patient at the time of gene therapy infusion will be described. Patient demographics and other baseline characteristics will be listed using the Safety population.

Demographic data will be determined using the following calculations:

**Age at Study day 1** = (Study day 1 visit date - date of birth + 1), expressed in days or

**Age at Study day 1** = (Study day 1 visit date - date of birth + 1)/30, expressed in months

**Height/Length** (in cm) = height (in inches) \* 2.54

**Weight** (in kg) = weight (in lbs) \* 0.4536

The following statistics regarding the patient's characteristics at birth will be described including but not limited to, ethnicity, race, gestational age (weeks), birth weight (kg), birth length (cm), and head circumference (cm).

Medical history data will be presented using body systems and conditions/diagnoses as captured on the eCRF. The body systems will be presented in alphabetical order and the conditions/diagnoses will be presented in alphabetical order within each body system.

The presence of significant medical conditions obtained from medical history will be described. In particular, the following parameters will be reported regarding symptoms and history of Spinal Muscular Atrophy: age at symptom onset (if applicable), baseline SMA symptoms (if applicable), family history of SMA, and number of siblings affected by SMA.

Patient baseline characteristics, including but not limited to CHOP-INTEND total score, levels of feeding, ventilatory and respiratory support, results from swallowing test, and lab results, will be summarized on the Safety population.

## **2.4 Treatments (study treatment, rescue medication, concomitant therapies, compliance)**

### **2.4.1 Study treatment / compliance**

The actual, weight-adjusted dose, in vg/kg, of OAV101 administered during the infusion will be reported, as well as the, duration of infusion, whether the entire volume was delivered, and whether the infusion was interrupted.

---

#### **2.4.2 Prior, concomitant and post therapies**

Prior and concomitant medications will be described. A prior medication is defined as any medication taken in the two weeks prior to the date of the gene therapy infusion of study drug. A concomitant medication is defined as any medication that started prior to the date of the infusion of study drug and continued to be taken after the infusion of study drug or any medication that started on or after the date of the infusion of study drug. A listing of patients in the safety population taking prior or concomitant medications will be provided by generic drug name based on the WHO Drug Dictionary together with ATC levels.

To reduce the host immune response to the AAV-based therapy, patients will receive prophylactic prednisolone at approximately 2 mg/kg/day on Day -1, Day 1, and Day 2, and then 1 mg/kg/day starting on Day 3 and until at least 30 days post-OAV101 infusion. After 30 days of treatment, the dose of prednisolone can be tapered for patients whose ALT values, AST values, are  $\leq 2$  X ULN for ALT and AST in accordance with the following treatment guideline:

- Weeks 5 and 6: 0.5 mg/kg/day
- Weeks 7 and 8: 0.25 mg/kg/day
- Week 9: prednisolone discontinued

The total number of days receiving prednisolone and total cumulative dose of prednisolone administered during the entire study (mg/kg\*days) will be computed for each patient.

To compute total cumulative dose, the total dosing period is subdivided into dosing intervals represented by constant dose levels. On the day of a dosage change, the entire day is represented under the new dosing interval at the new dose.

Non-medication Therapies/Procedures will be defined as “Prior” and/or “Concomitant”. Prior Non-medication Therapies/Procedures are defined as therapies or procedures started prior to injection of OAV101. Concomitant Non-medication Therapies/Procedures are defined as therapies or procedures ongoing at time of injection of OAV101 or started after the injection.

A listing of Non-medication Therapies/Procedures will be provided.

#### **2.5 Analysis supporting primary objective(s)**

Primary efficacy endpoints will be presented in data listings and patient profiles where patients will be identified as to the analysis set(s) to which they belong.

For completeness, the remainder of the section is only for information purpose.

##### **2.5.1 Primary endpoint(s)**

Developmental milestones will be assessed/determined by the qualified Clinical Evaluators at the investigational sites. The assessments will be captured on video from two camera angles.

---

The videos will then be reviewed and verified by an independent, external reviewer for concordance. Only milestones confirmed by the independent reviewer will be utilized for the primary endpoint.

The primary efficacy endpoint is of symptomatic SMA Type 1 patients who are homozygous negative for SMN1 exon 7 and have 2 copies of SMN2 without the SMN2 genetic modifier that achieve the ability to sit without support for at least 10 seconds at any visit up to and including the 18 months of age visit. It is defined by the World Health Organization Multicentre Growth Reference Trial (WHO MGRS), confirmed by video recording, [REDACTED]

[REDACTED]  
[REDACTED]

Primary endpoint data will be listed for the ITT population.

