14.4.2. Primary and Secondary Efficacy Analysis

Primary and secondary efficacy endpoints will be presented in data listings where patients will be identified as to the analysis set(s) to which they belong. Endpoints defined as proportions will be presented as a dichotomous outcome for each patient.

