### **2.6 Analysis supporting secondary objectives**

Secondary efficacy endpoints will be presented in data listings and patient profiles where patients will be identified as to the analysis set(s) to which they belong. For completeness, the remainder of the section is only for information purpose.

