#### **2.6.1 Secondary endpoint(s)**

The secondary efficacy endpoint, event-free survival, is defined as avoidance of any one of the following events up to 14 months of age, whichever occurred first:

- Death, *or*
- Tracheostomy, *or*
- Noninvasive Ventilatory support  $\geq$ 16-hour per day *and* continuously  $\geq$ 14 days

---

Usage data for patients using non-invasive ventilatory support will be extracted directly from the device ( [REDACTED] ) on an SD card, or USB stick and transferred as an external dataset. Average daily use of non-invasive ventilatory support at baseline, Days 7, 14, 21, 30 and monthly thereafter will be calculated. In the event that data cannot be extracted from an SD card, usage recorded in the electronic case report form may be analyzed. If a patient did not have a device with the capability to record usage data at baseline and was using non-invasive ventilatory support prior to screening, the average daily usage will be based on parent report and documented in the source documentation. As a secondary analysis, the amount of ventilation support will be categorized into None, >0-≤12 hours, >12-<16 hours, ≥16 or permanent ventilation. At each of the above time points, the count and percent of patients in each ventilation support category will be presented.

Secondary endpoint data will be listed for the ITT population.

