**Table 7: Third Percentile Weights for Age and Gender**

Age	Gender	Weight (kg)
14 months	Male	8.2
	Female	7.5
18 months	Male	8.9
	Female	8.2

Reference: [http://www.who.int/childgrowth/standards/Technical\\_report.pdf](http://www.who.int/childgrowth/standards/Technical_report.pdf) (Table 39 and Table 50).

- Achievement of Developmental Milestones is based on video confirmed central reviewed at any visit during the study.

Exploratory endpoint data will be presented in data listings and patient profiles for the ITT population and, where appropriate, for the Ability to Thrive ITT population.

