## 4 Change to protocol specified analyses

Due to the narrowed scope of COAV101A12304 (AVXS 101 CL 306) and limited subjects enrolled, only individual data listings and patient profiles will be generated, with the exception of three AE summary tables. There are no changes to analyses planned in protocol version 6.0.

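### Could the ITT sentences in the SAP keep a treated patient out of the efficacy listings that the protocol calls for?

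*SAP*

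**What the plan says.** Protocol 14.4.2 sends the primary and secondary endpoints to listings that show each patient's analysis set(s), and adds: "Endpoints defined as proportions will be presented as a dichotomous outcome for each patient". It names no population. The statistical part of the protocol synopsis, and Protocol 14.1, put the exploratory endpoints into listings as well, without naming a population or asking for set flags.

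SAP 2.5 and 2.6 open by repeating the flag rule for listings and patient profiles, "where patients will be identified as to the analysis set(s) to which they belong". Both openings then limit the force of what follows; in 2.5 the words are: "For completeness, the remainder of the section is only for information purpose". Inside that remainder, SAP 2.5.1 says "Primary endpoint data will be listed for the ITT population" and SAP 2.6.1 says "Secondary endpoint data will be listed for the ITT population".

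SAP 2.12, below Table 7, says "Exploratory endpoint data will be presented in data listings and patient profiles for the ITT population" and adds the Ability to Thrive ITT set where suitable. It carries no such notice.

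SAP 2.2 defines ITT as "symptomatic patients with biallelic deletion mutations of SMN1 (exon 7/8 common homozygous deletions) and 2 copies of SMN2", without the modifier and dosed before 180 days of age. All Enrolled means every dosed patient. SAP 4 states: "There are no changes to analyses planned in protocol version 6.0".

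**The concern.** ITT is narrower than enrolment. Inclusion criterion 1 (Protocol 8.1) admits one SMN2 copy, point mutations and modifier carriers, and sets no symptom requirement. A patient could therefore be dosed and fall outside ITT.

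The flag rule also sits awkwardly with an ITT-only listing. Every ITT patient is also in the All Enrolled and Safety sets, so those three flags would be the same on every row and only Ability to Thrive membership could vary. That suggests the rule was written with all dosed patients in view. Where the SAP plainly wants every dosed patient, it names All Enrolled or Safety (2.3, 2.3.2, 2.4.2, 2.7); no efficacy sentence does so.

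The stake is that the SAP plans no efficacy analysis beyond listings and profiles. On the ITT-only reading, a dosed patient outside ITT would have no listing for sitting, ventilation-free survival or exploratory efficacy. Two programmers might then produce different output from the same SAP, and a narrowing of the protocol would have gone unrecorded in SAP 4.

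**Working it through.** The plan gives no figure to reproduce here and tests no hypothesis. The check is a comparison of texts and a count of patients.

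**1. Routes outside ITT.** Setting Protocol 8.1 against SAP 2.2 gives four: one SMN2 copy, a point mutation, the modifier, no symptoms. Age is not a fifth, because both texts require dosing before 180 days. The concern is right that the sets differ.

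**2. Size.** Protocol 7.2 gives 2 enrolled patients. With k of them outside ITT, the share without an efficacy listing on the ITT-only reading is k/2:

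| k | Share |
|---|---|
| 0 | 0/2 = 0% |
| 1 | 1/2 = 50% |
| 2 | 2/2 = 100% |

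These are all the values possible with two patients. They bound the effect but give no evidence that k is above 0. The documents do not give either patient's genotype or symptom status.

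**3. Which sentences can conflict with the protocol.**

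| SAP section | Endpoint | Under an informational notice? | Covered by the Protocol 14.4.2 flag rule? |
|---|---|---|---|
| 2.5.1 | primary | yes | yes |
| 2.6.1 | secondary | yes | yes |
| 2.12 | exploratory | no | no |

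The two sentences that could contradict Protocol 14.4.2 are the two that the SAP labels informational, and their lead-ins carry the protocol's rule forward. The one sentence without that label deals with endpoints that 14.4.2 does not cover. No row has both a binding ITT restriction and a protocol rule for it to breach.

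**4. Who has an endpoint value.** Protocol 14.1.1 and 14.1.2 limit the primary and secondary endpoints to symptomatic patients who lack SMN1 exon 7 on both copies and have two SMN2 copies without the modifier. A patient outside that group has no value on these endpoints as defined. An outcome for each patient can fairly be read as each patient to whom the endpoint applies, so the ITT sentences largely restate the endpoint.

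**5. What would still be shown for a non-ITT patient.** Study status at 14 and 18 months (SAP 2.3.1), baseline CHOP INTEND and levels of feeding and ventilatory support (2.3.2), non-medication procedures (2.4.2), all safety data (2.7) and deaths (2.7.2) carry no ITT limit. SAP 1 describes its coverage as including listings of all data, effectiveness among them. SAP 2.1 and 4 promise individual listings and profiles without naming ITT.

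**The case for a change.** The best argument for acting is that neither reading of 2.5.1 and 2.6.1 is comfortable. If those sentences do not bind, no binding sentence names a population for the primary and secondary listings. If they do bind, they narrow a protocol rule that names none, while SAP 4 reports no change. A one-line clarification would cost almost nothing: at most two patients' rows per listing and no protocol amendment.

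Part of this stands. The text does not expressly say whether a dosed patient outside ITT is printed, and an all-dosed listing with flags makes better use of the flag rule. For exploratory data, the plain reading of 2.12 would omit such a patient. Whether that is sensible cannot be judged endpoint by endpoint, because the exploratory endpoints are blacked out.

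The argument that output would be lost or misleading does not stand. An omitted patient would be one the primary and secondary endpoints already exclude. The facts should also have been known when the scope was written: enrolment had closed by 11 November 2020 (Protocol 7.2), genetic reconfirmation was compulsory for every patient at screening or before the next visit (Protocol 12.1.10), and the SAP is dated 30 July 2021, before database lock. Stating that non-ITT patients are left out would resolve the ambiguity just as well, so the choice between the two displays is one of preference.

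**Conclusion.** The ambiguity is real but minor, and the plan can stand. It concerns which rows are printed for 0, 1 or 2 of 2 patients. No estimate, denominator, test or conclusion depends on it. If both patients meet the ITT definition, the two readings give identical listings.

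This rests on three points: the protocol's flag rule names no population; the primary and secondary endpoints carry essentially the ITT restrictions in their own definitions; and the notices in SAP 2.5 and 2.6 leave the flag rule as the operative instruction. It does not assume that both patients are in ITT, which the documents do not disclose. If one is not, following the SAP still gives correct output for the endpoints as defined. An analyst with two patients' data can print both with their set flags under the 2.5 and 2.6 lead-ins, and nothing in the protocol stands in the way.

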#### **2.5.2 Statistical hypothesis, model, and method of analysis**

Not applicable.

#### **2.5.3 Handling of intercurrent events**

Not applicable.

#### **2.5.4 Handling of missing values not related to intercurrent event**

Not applicable.

#### **2.5.5 Sensitivity analyses**

Not applicable.

#### **2.5.6 Supplementary analyses**

Not applicable.

### **2.6 Analysis supporting secondary objectives**

Secondary efficacy endpoints will be presented in data listings and patient profiles where patients will be identified as to the analysis set(s) to which they belong. For completeness, the remainder of the section is only for information purpose.

#### **2.6.1 Secondary endpoint(s)**

The secondary efficacy endpoint, event-free survival, is defined as avoidance of any one of the following events up to 14 months of age, whichever occurred first:

- Death, *or*
- Tracheostomy, *or*
- Noninvasive Ventilatory support  $\geq$ 16-hour per day *and* continuously  $\geq$ 14 days

---

Usage data for patients using non-invasive ventilatory support will be extracted directly from the device ( [REDACTED] ) on an SD card, or USB stick and transferred as an external dataset. Average daily use of non-invasive ventilatory support at baseline, Days 7, 14, 21, 30 and monthly thereafter will be calculated. In the event that data cannot be extracted from an SD card, usage recorded in the electronic case report form may be analyzed. If a patient did not have a device with the capability to record usage data at baseline and was using non-invasive ventilatory support prior to screening, the average daily usage will be based on parent report and documented in the source documentation. As a secondary analysis, the amount of ventilation support will be categorized into None, >0-≤12 hours, >12-<16 hours, ≥16 or permanent ventilation. At each of the above time points, the count and percent of patients in each ventilation support category will be presented.

Secondary endpoint data will be listed for the ITT population.

#### **2.6.2 Statistical hypothesis, model, and method of analysis**

Not applicable.

#### **2.6.3 Handling of intercurrent events**

Not applicable.

#### **2.6.4 Handling of missing values not related to intercurrent event**

Not applicable.

#### **2.6.5 Sensitivity analyses**

Not applicable.

#### **2.6.6 Supplementary analyses**

Not applicable.

### **2.7 Safety analyses**

Safety will be assessed through the incidence and severity of AEs, vital sign assessments, cardiac assessments, laboratory evaluations (chemistry, hematology, immunology, urinalysis), physical examinations, and use of concomitant medications. Adverse events will be coded in accordance with the most current version of the MedDRA coding dictionary. Safety assessments will be presented in data listings or patient profiles for the safety population. In addition, summary tables will be prepared for treatment-emergent AEs and SAEs together with an overview of AEs.

#### **2.7.1 Adverse events (AEs)**

All adverse events will be assessed for their seriousness, relatedness to study treatment, relationship to study discontinuation, and severity according to CTCAE version 4.03 criteria.

---

Adverse event data will be summarized and presented using primary MedDRA system organ classes (SOCs) and preferred terms (PTs) according to the version of the MedDRA coding dictionary used for the study at the time of database lock. The actual version of the MedDRA coding dictionary used will be noted in the clinical study report. The system organ classes will be presented in alphabetical order and the preferred terms will be presented in alphabetical order within each system organ class.

The following summaries of adverse events will be generated:

- Treatment-emergent adverse events;
- Serious treatment-emergent adverse events.

For all adverse event summaries, the number of treatment-emergent adverse events, the number and percentage of patients experiencing treatment-emergent adverse events will be tabulated according to SOC and PT. Patients reporting more than one adverse event for a given PT will be counted only once for that term (most severe incident for the severity tables and most related incident for the relationship tables). Patients reporting more than one adverse event within a SOC will be counted only once for that SOC. Patients reporting more than one adverse event will be counted only once in the overall total.

An overview of adverse events will be presented consisting of the number and percentage of patients experiencing at least one event for the following adverse event categories:

- Any adverse event;
- Any serious adverse event;
- Any treatment-emergent adverse event;
- Treatment-emergent adverse events with a "possibly related", "probably related", "definitely related" of being related to OAV101
  - Any AE reported as Possibly, Probably, or Definitely Related will be consolidated into a single category and summarized as "Related" in the tables
  - Any AE reported as Unlikely Related or Unrelated will be consolidated into a single category and summarized as "Not Related" in the tables
- Grade 3 and 4 treatment-emergent adverse events;
- Any serious treatment-emergent adverse events;
- Serious treatment-emergent adverse events "related" to OAV101;
- Treatment-emergent adverse events leading to discontinuation of patient from study;
- Treatment-emergent adverse events leading to death;
- Treatment-emergent adverse events of special interest (cp. Section 2.7.1.1);
- Deaths.

---

### **2.7.1.1 Adverse events of special interest / grouping of AEs**

The following are considered AEs of special interest (AESIs):

- Hepatotoxicity
- Thrombocytopenia
- Cardiac adverse events
- Sensory abnormalities suggestive of ganglionopathy
- Thrombotic microangiopathy

Primarily defined by using Standard MedDRA queries (SMQ), AESIs are identified as follows:

Hepatotoxicity as hepatic disorders (SMQ), thrombocytopenia as transient thrombocytopenia (CMQ), sensory abnormalities suggestive of ganglionopathy as DRG cell inflammation (CMQ), and cardiac events as ischemic heart disease (SMQ) or cardiomyopathy (SMQ) or cardiac arrhythmias (SMQ) or embolic and thrombotic events (SMQ) or myocardial infarction (SMQ), respectively.

Thrombotic microangiopathy is identified via the following approach:

- Criteria #1: cases with any one of the following PTs: thrombotic microangiopathy OR haemolytic uraemic syndrome OR atypical haemolytic uraemic syndrome (i.e. A).
- Criteria #2: cases with at least one PT from EACH of the following SMQs representing thrombocytopenia, hemolysis and relevant renal events respectively:
  - Haematopoietic thrombocytopenia (SMQ) (i.e. B)
  - Haemolytic disorders (SMQ) (i.e. C)
  - Acute renal failure (SMQ)(i.e. D) OR Renovascular disorders (SMQ) (i.e. E)

